1.0 PROTOCOL SUMMARY AND SCHEMA

Triple negative breast cancer patients with metastatic or unresectable, locally advanced disease who require radiation therapy to a measurable tumor site are eligible. Prior to treatment, all patients will receive a biopsy of the tumor to be irradiated. Utilizing the Memorial Sloan Kettering Homologous Recombination Repair (MSK-HRR) Assay, patients will be identified as either HR-deficient or HR-proficient. Knowledge of the HR repair status prior to treatment is not necessary, since all patients in the study will receive the same treatment, regardless of the knowledge of the tumor- concurrent cisplatin and radiation (RT) to the tumor.

The primary purpose of the trial is to assess whether or not HR repair status is a sensitive biomarker of response, as measured by complete response (CR) rate in patients receiving cisplatin and radiation. Cisplatin will be given once a week(+ 3 days) for 1-2 weeks, followed by concurrent delivery with RT to the tumor. Following the completion of RT, pending no toxicities, but prior to the week 12 post RT evaluable timepoint, patients will continue to receive cisplatin or until POD, based on MD discretion.

Secondary objectives are to assess time to progression and overall response rate (CR+PR+SD) by HRR status. Exploratory objectives are to assess association between tumor infiltrating lymphocyte (TIL) and treatment response and to compare the effectiveness of RECIST 1.1 criteria with PET Response Criteria in metabolically active tumors.

At baseline, all patients will receive PET-CT. An MR will be obtained in addition only if the study radiologist determines that tumor is insufficiently evaluable with PET-CT. At 12 +2 weeks after completion of RT, patients will undergo the same imaging modality used at baseline assessment (PET-CT or MR) in order to assess treatment response. The target accrual is 54 patients, to be achieved within 3.5 years.

¹ Patients with biopsy-proven TNBC requiring locoregional control or palliation with radiation to a measurable tumor.

² Obtain study staging only if unavailable 28 days prior to study registration. All patients will receive baseline PET-CT performed at MSKCC. An MR will be added if PET-CT is deemed to be insufficient for tumor evaluation by the study radiologist at baseline evaluation.

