2.0 OBJECTIVES AND SCIENTIFIC AIMS

The primary objective of this trial is to evaluate the performance of the MSK-HR repair assay as a biomarker in predicting response to concurrent cisplatin and RT in breast cancer patients with measurable metastatic or unresectable, locally advanced disease. Radiographic complete response (CR) of the irradiated tumor will be counted as a positive response to treatment. Radiographic response less than a CR, progression of the irradiated tumor or appearance of a new lesion within the irradiated field will be categorized as a failure to respond to treatment. All other sites of metastatic disease that is outside of the irradiated field will be monitored and counted toward disease progression.

Secondary objectives are to assess:

- Partial response, stable disease and progression of disease within the irradiated tumor as well as systemically (in sites distant to the irradiated tumor)
- Overall time to progression
- Toxicities of concurrent cisplatin and radiation

Exploratory objectives are to assess:

- Examine immune correlates to determine the impact of treatment on anti-tumor immunity and as a predictor of treatment response
- Determine the sensitivity of ctDNA detection in patients receiving chemoradiation for metastatic and locally recurrent TNBC
- Compare the efficacy of RECIST 1.1 vs. PET Response Criteria (PRC) as measurement tools for treatment response

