Finally, the PrECOG 0105 study included 80 TNBC and BRCA1/2 mutated patients treated with neoadjuvant carboplatin, gemcitabine and iniparib [38]. Pathologic CR was achieved in 36% of the overall population, 47% in the BRCA1/2 mutated population and 56% in triple negative patients who also had BRCA 1/2 mutations. The toxicity profile was more favorable than that of the Gepar Sixto regimen, with myelosuppression (grade 3 or 4 neutropenia in 49%) and elevations in liver enzymes (grade 3 in 24%).

Whereas the aforementioned trials evaluated platinum chemotherapy in the neoadjuvant setting, the efficacy of platinum chemotherapy has also been studied in metastatic TNBC patients. TBCRC 009 was a multicenter single-arm phase I study of single-agent platinum in 86 patients with metastatic TNBC [39]. Patients received cisplatin 75mg/m² or carboplatin AUC=6 every 3 wks, by physician choice. The objective response rate (ORR) was 30.2% overall, including 4 CR (4.7%), 22 PR (25.6%). The ORR was 54.5% vs. 19.7% in BRCA1/2 carriers (n=11) vs. non-carriers (n=66); ($p=0.02$). Six long-term responders remain disease-free at median follow up of 4 yrs, 3 of whom stopped treatment after 6 cycles. Exploratory subgroup analysis of RR: Cisplatin 37%, Carboplatin 23%; 1st line therapy 31.7%, 2nd line therapy 20%. 33% of pts progressed by 6 weeks, but 33% remained on study for ≥ 6 mos. 51 treatment-related grade 3/4 toxicities occurred. 2 patients had grade 4 toxicities (neutropenia (1) and hypertension (1)), while the others were grade 3 (fatigue (8), neutropenia (6), anemia (5), hyponatremia (4)).

In a subsequent analysis presented at the ASCO 2014 Annual Meeting, predictors of response to platinum chemotherapy were assessed, including p63/p73 expression by RT-PCR as a predictor of response. Tumor-based exploratory studies included gene expression (GE) profiling, PIK3CA and p53 mutational status, and homologous recombination deficiency (HRD) assays correlating with

BRCA1/2 inactivation. All biomarkers *except* the HRD assays failed to predict responses to platinum chemotherapy. Types of HRD assays performed included Loss of Heterozygosity (LOH), Telomere Allelic Imbalance (tAI), and Large-scale State Transition (LST). Among the small group of 22 patients with available tissue, scores in all of the HRD assays were higher in BRCA1/2 carriers than non-carriers, and in responders than non-responders (HRD-LST responders vs. nonresponders, $p=0.0016$).

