12.0 CRITERIA FOR THERAPEUTIC RESPONSE/OUTCOME ASSESSMENT

Response to radiation and chemotherapy treatments will be using the Reviewed Response Evaluation Criteria in Solid Tumors (RECIST) guidelines version 1.1 . However there are limitations in using anatomic response criteria alone, particularly when evaluating bone metastases without an extra-osseous component, which is common in breast cancer patients. “PERCIST” (PET Response Criteria in Solid Tumors), is a commonly proposed method for measuring treatment response based on metabolic response criteria with PET [68]. A limitation of PERCIST is that it only takes into account the single hottest lesion and it relies upon SUV peak measurements, which are not easily reproducible in lesions with low FDG-avidity, as are often found in breast cancer. Since there are no standardized methods for quantifying FDG-tracer avidity in individual tumor lesions, we will use a modification of PERCIST criteria called “PET Response Criteria” (PRC) that is currently being utilized in other cancer protocols at MSK requiring metabolic assessment. In brief, the SUVmax of the tumor to be irradiated will be measured and recorded. On subsequent studies, the same target lesion will be measured and recorded. Lesions where SUVmax is no greater than background will be recorded as zero.

Response or progression will be graded as follows:

CR: All lesions no greater than background SUVmax

PR: SUVmax decreased by $\geq 30\%$ greater than background

SD: Lesions that do not fit criteria for response or progression

PD: SUM SUVmax increased by $\geq 30\%$ or development of a new lesion within the radiated field

Radiological review will be conducted by the study radiologists. PET-CT will be obtained in all patients at baseline. In general, PRC will be preferred over RECIST 1.1 for response assessment, except in cases where the tumor target is not clearly defined on PET-CT (e.g. lesions obscured by areas of physiologic FDG-avidity). In such cases, the study radiologists will decide when baseline images are available whether or not to use PRC or RECIST 1.1. If PET-CT evaluation is determined to be insufficient for tumor evaluation, MR will be recommended. The same imaging study (PET-CT or MR) or response criteria (PRC or RECIST 1.1) used at baseline assessment will be utilized for the follow-up assessments of the irradiated tumor.

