However, we will plan to accrue a total of **62** patients in order to allow for early dropout due to disease progression/death prior to response evaluation, or inability to obtain HRR status from the core biopsy. For the primary analysis, all patients for whom HRR status can be ascertained will be included in the denominator. Patients who progress or die prior to the response evaluation at 12 +/- 2 weeks post-RT will be included as failures. This includes patients with disease progression outside of the irradiated tumor. Patients for whom HRR status cannot be ascertained or who left the study for nondisease related reasons will be replaced.

A secondary analysis of interest is to evaluate the CR rate among the subset of patients who are able to complete the planned study treatment and have a scan at the 12 +/- 2 week post-RT time point. Radiographic complete response (CR) of the irradiated tumor will be counted as a positive response to treatment. Radiographic response less than a CR, progression of the irradiated tumor or appearance of a new lesion within the radiated field will be categorized as a failure to respond to treatment. All other sites of metastatic disease that is outside of the irradiated field will be monitored and counted toward disease progression.

Based on prior experience with the HRR assay, we estimate that approximately 10% of patients will either 1) not have a definitive HRR status, or 2) will not complete the planned study treatment or 3) not have a response assessment at 12-14 week time point. To ensure we have 80% power for both the primary and secondary analyses we have added 8 patients to the sample size for a total of 62. The accrual number has been adjusted to 54 patients.

We expect to accrue 1 to 2 patients per month, or approximately 18 patients per year. Thus, accrual for the trial will be completed in 3.5 years. Based on previous data on the tolerability of cisplatin and radiation extrapolated from head and neck and gynecologic malignancies, we do not anticipate toxicities associated with the study treatment and as such, we have not incorporated an early stopping rule.

Secondary endpoints include overall response rates (CR+PR+stable disease), time to progression and CTCAE v4.0 toxicities. These endpoints will be compared by HRR status using the log-rank test for time-to-event endpoints and Fisher's exact test for binary endpoints.

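### The secondary overall response rate counts stable disease as response, against the protocol's own response criteria, and no CR+PR comparison by HRR status is planned

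*Combined protocol and SAP*

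**What the plan says.** The secondary endpoint is defined twice, in the same way. Section 1.0 (Protocol Summary) gives "overall response rate (CR+PR+SD) by HRR status". Section 14.0 (Biostatistics) gives "Secondary endpoints include overall response rates (CR+PR+stable disease), time to progression and CTCAE v4.0 toxicities" and assigns Fisher's exact test to binary endpoints compared by HRR status.

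Section 12.0 sets the response grades. Under the PET Response Criteria (PRC), a partial response needs a fall in SUVmax of at least 30%. Progression needs a rise of at least 30% or a new lesion in the field. What is left is "SD: Lesions that do not fit criteria for response or progression".

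Section 3.4 describes the single-agent platinum trial in metastatic TNBC (TBCRC 009), which section 14.0 uses to inform the design CR rates: "The objective response rate (ORR) was 30.2% overall, including 4 CR (4.7%), 22 PR (25.6"%). The same section gives that trial's contrast by mutation status: "The ORR was 54.5% vs. 19.7% in BRCA1/2 carriers (n=11) vs. non-carriers (n=66").

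Section 2.0 lists the secondary categories one by one, "Partial response, stable disease and progression of disease within the irradiated tumor as well as systemically (in sites distant to the irradiated tumor"), and defines no pooled rate.

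**The concern.** The protocol's grading puts stable disease outside response, and its endpoint definition then counts it as response. Among patients with a week-12 assessment, the pooled rate is one minus the proportion graded as progression. It does not distinguish a lesion that shrank from one that did not change.

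Two things are at stake. A reader who meets a response rate in the results will tend to read it as CR+PR, the sense used in section 3.4, and will take it as higher than it is. And the trial asks whether HRR status predicts response, yet between the strict CR endpoint and plain absence of progression no comparison is planned. The conventional CR+PR contrast by HRR status is missing from the list of analyses.

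**Working it through.** **1. The cited rate.** From the counts in section 3.4: CR 4/86 = 4.7%, PR 22/86 = 25.6%, and (4 + 22)/86 = 26/86 = 30.2%. This reproduces the stated figure, so the cited rate excludes stable disease.

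**2. Size of the difference.** Since (CR+PR+SD) − (CR+PR) = SD, the excess is exactly the stable-disease proportion. The documents give no SD rate for this trial or for the cited one. Section 3.4 does say that 33% of the cited trial's patients had progressed by 6 weeks. If everyone else was CR, PR or SD (assumption), the pooled rate there could be at most 100% − 33% = 67%. Adding SD could therefore move 30.2% by anything from 0 to 67.0 − 30.2 = 36.8 points.

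**3. What falls inside SD.** With PRC cut-offs at a 30% fall and a 30% rise, a lesion whose SUVmax is up 29%, with no new in-field lesion, is SD. It is counted in the response numerator.

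**4. Effect on the HRR comparison.** For assessed patients, CR+PR+SD = 1 − PD, so the difference between HRR groups in the pooled rate is the difference in progression with its sign reversed. If HRR deficiency moved patients from SD to PR or CR and left progression unchanged, the pooled difference would be zero, however large the CR+PR difference.

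**5. Power under stated assumptions.** At 40% deficiency, 0.4 × 54 = 21.6, so 22 HRR-deficient and 32 HRR-proficient patients. Power of Fisher's exact test at 5%, by full enumeration (the plan does not state sidedness for secondary endpoints, so both are shown):

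| Endpoint and assumed rates | One-sided | Two-sided |
|---|---|---|
| CR+PR, 54.5% vs 19.7% (the cited mutation split, assumed for HRR) | 77.8% | 71.4% |
| CR+PR+SD, 95% vs 85% | 14.9% | 7.9% |
| CR+PR+SD, 90% vs 75% | 27.3% | 20.0% |
| CR+PR+SD, 90% vs 67% | 51.2% | 43.6% |
| CR+PR+SD, 95% vs 60% | 89.9% | 85.8% |

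The pooled endpoint has low power when both groups are near 100% and good power when a 35-point gap remains. The documents do not say which applies.

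**6. The plan's power table.** The stated 85%, 83% and 80% are for CR at 65% vs 30%. A one-sided z-test with unpooled variance reproduces them (85.0%, 83.2%, 80.4%). They do not involve the secondary rate, for which the plan gives no expected value or power.

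**The case against.** The strongest reply is that nothing is hidden. The composition is spelled out both times the rate is defined, and a trial may define its own composite differently from a study it cites. Section 2.0 already lists PR, SD and progression separately, so with CR as the primary endpoint a reader could derive CR+PR. This stands in part: the composition is disclosed and the data will exist. It does not remove the conflict with section 12.0, which is internal to the protocol, and it does not supply the missing CR+PR comparison by HRR status.

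A reader might infer that the pooled rate must land near its ceiling, say 85–95%, and so cannot separate the HRR groups. That range needs in-field progression of 5–15% at week 12, a figure found nowhere in the documents. It also needs the rate to cover the irradiated tumor only, which section 14.0 does not say; the secondary objectives in section 2.0 extend to distant sites. The only progression figure available, 33% by 6 weeks on platinum without radiation, points to about 67% or lower if systemic disease counts. Here the assessment comes about 16–19 weeks after cisplatin starts: 1–2 weeks of lead-in, 3–5 of radiation, then 12, before any boost or the two-week window.

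A reader might also infer that a planned comparison with the cited trial is invalidated. None is planned; section 14.0 uses that trial only for the primary CR assumptions. Nor would CR+PR make the two directly comparable, since this trial adds radiation and relies mainly on PRC.

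**Conclusion.** The point holds as a fault in definition and in the list of analyses. Sections 1.0 and 14.0 count as responders patients whom section 12.0 grades as non-responders. The reported rate exceeds CR+PR by the full SD share, and CR+PR is not compared by HRR status. These conclusions need no assumption.

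The size of the excess in this trial cannot be stated, because no SD rate is given. In the cited trial it could be at most about 37 points, assuming that everyone who had not progressed by 6 weeks was CR, PR or SD. Loss of sensitivity is possible but conditional on progression rates and on anatomical scope, neither of which is documented. It should not be read as established.

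Nor should the point be read as touching the primary analysis. That endpoint is CR alone, and the sample size and power table rest on it.

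**What to change.** In sections 1.0 and 14.0, define overall response as CR+PR and compare it by HRR status with the Fisher's exact test already planned for binary secondary endpoints. Keep CR+PR+SD as a separate row labelled disease control rate. For each rate, state whether it covers the irradiated tumor only or systemic disease as well.

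Section 12.0 already grades every category needed for the irradiated tumor, so for that scope no new scans, visits or patients are required. The cost is a change of wording, one extra table row, and a reported response rate that is lower by the stable-disease share.

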15.1 RESEARCH PARTICIPANT REGISTRATION AND RANDOMIZATION PROCEDURES

15.2 Research Participant Registration

Confirm eligibility as defined in the section entitled Inclusion/Exclusion Criteria. Obtain informed consent, by following procedures defined in section entitled Informed Consent Procedures. During the registration process registering individuals will be required to complete a protocol specific Eligibility Checklist. The individual signing the Eligibility Checklist is confirming whether or not the participant is eligible to enroll in the study. Study staff are responsible for ensuring that all institutional requirements necessary to enroll a participant to the study have been completed. See related Clinical Research Policy and Procedure #401 (Protocol Participant Registration)

15.3 Randomization

There is no randomization.

16.1 DATA MANAGEMENT ISSUES

A Clinical Research Coordinator (CRC) from the Department of Radiation Oncology (Breast Service) will be assigned to the study. The responsibilities of the CRC include project compliance, data collection, abstraction and entry, data reporting, regulatory monitoring, problem resolution and prioritization, and coordinating the activities of the protocol study team.

The data collected for this study will be entered into a secure database (Clinical Research Database—CRDB). Source documentation will be available to support the computerized patient record.

16.2 Quality Assurance

Regular registration reports will be generated to monitor patient accruals and completeness of registration data. Routine data quality reports will be generated to assess missing data and inconsistencies. Accrual rates and extent and accuracy of evaluations and follow-up will be monitored periodically throughout the study period and potential problems will be brought to the attention of the study team for discussion and action. Random-sample data quality and protocol compliance audits may be conducted by the study team, at a minimum of once per year, more frequently if indicated.

16.3 Data and Safety Monitoring

The Data and Safety Monitoring (DSM) Plans at MSKCC were approved by the NCI in September 2001. The plans address the new policies set forth by the NCI in the document entitled "Policy of the

National Cancer Institute for Data and Safety Monitoring of Clinical Trials", which can be found at <http://cancertrials.nci.nih.gov/researchers/dsm/index.html>. The DSM Plans at MSKCC were established and are monitored by the Office of Clinical Research. The MSKCC DSM Plans can be found on the MSKCC Intranet at<https://one.mskcc.org/sites/pub/clinresearch/Documents/MSKCC%20Data%20and%20Safety%20Monitoring%20Plans.pdf>. There are several different mechanisms by which clinical trials are monitored for data, safety, and quality. There are institutional processes in place for quality assurance (e.g. protocol monitoring, compliance and data verification audits, therapeutic response, and staff education on clinical research QA) and departmental procedures for quality control, plus there are two institutional committees that are responsible for monitoring the activities of our clinical trials programs. The committees: Data and Safety Monitoring Committee (DSMC) for Phase I and II clinical trials, and the Data and Safety Monitoring Board (DSMB) for Phase III clinical trials, report to the Center's Research Council and Institutional Review Board. During the protocol development and review process, each protocol will be assessed for its level of risk and degree of monitoring required. Every type of protocol (e.g., NIH sponsored, in-house sponsored, industrial sponsored, NCI cooperative group, etc.) will be addressed and the monitoring procedures will be established at the time of protocol activation.

17.1 PROTECTION OF HUMAN SUBJECTS

Describe in detail the information that would be relevant to an IRB reviewer as to how the study will protect the rights of human subjects. This should include, but not limited to the following: risks, benefits, toxicities/side effects, alternatives/options for treatment, financial costs/burdens. Privacy and confidentiality, adverse event reporting, voluntary nature of the study, and more.

17.2 Privacy

- MSK's Privacy Office may allow the use and disclosure of protected health information pursuant to a completed and signed Research Authorization form. The use and disclosure of protected health information will be limited to the individuals described in the Research Authorization form, including members of research teams at participating sites such as [name]. The following will be shared:
 - Patient identifiers including full name, date of birth, and date of assessments
 - Data collected during protocol visits and assessments
- A Research Authorization form must be completed by the Principal Investigator and approved by the IRB and Privacy Board (IRB/PB).
- The consent indicates that individualized de identified information collected for the purposes of this study may be shared with other qualified researchers. Only researchers who have received approval from MSK will be allowed to access this information which will not include protected health information, such as the participant's name, except for dates. It is also stated in the Research Authorization that their research data may be shared with other qualified researchers.

